If participants instill *Lactobacillus* at any time during the intervention phase, and after *Lactobacillus* instillation reports a UTI as an Adverse Event (AE) we will request their urinalysis and urine culture results to attempt to determine if *Lactobacillus* might have been the cause of the UTI. If determined necessary by the PI, Co-PI and/or DSMB other AEs reported could require retrieval of medical records.

Phase III: Pilot Study of Multiple (up to 2) *Lactobacillus* Bladder Instillations

We will recruit 30 persons in whom we will collect urine up to 18 timepoints (up to monthly for the first year when not experiencing symptoms, up to two times when subject experience urinary symptoms, follow-up after either *Lactobacillus* treatment or antibiotics, and three (3) months into the six (6) months follow-up) in order to **estimate the strength of the associations between successful implementation of the probiotic self-management program and urinary symptoms, bladder inflammation, and the urine microbiome.** We will conduct an 18-month study in which each participant will serve as his/her own control through 3 phases of study: 6-months usual care (baseline), 6-months probiotic intervention, and 6-months follow-up
Study Design: We will recruit N=30 subjects with neuropathic bladder who will contribute urine samples for analyses.

Clinical Setting: MedStar National Rehabilitation Hospital and Children's National Medical Center.

Target Enrollment: 30 adult subjects at least 1-year post-injury and 18 years of age with SCI/MS or at least 18 years of age with SB

Recruitment Strategy: SCI/MS and SB subjects will be enrolled with assistance from United Spinal Association. Additionally, we will query the MedStar National Rehabilitation Hospital inpatient service, the 40+ MedStar National Rehabilitation Network outpatient sites, various MedStar Network databases, and the CNMC Spina Bifida database. Databases will be queried for participants who meet the eligibility criteria and have already provided HIPAA authorization and consent to be contacted for future research. Announcements and IRB-approved flyers will be posted on the United Spinal Association and study websites and at participating institutions.

Informed Consent: Consent will be obtained by the PI, Study Coordinator, or Research Assistant. All project staff are currently CITI certified and have passed all requirements for HIPAA certifications.

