following urinary symptoms is required for UTI diagnosis in patients using intermittent catheterization: new onset or worsening fever, rigors, altered mental status, malaise, lethargy with no other identified cause, flank pain, costovertebral angle tenderness, acute hematuria, pelvic discomfort, increased spasticity, autonomic dysreflexia or sense of unease. The Guidelines specifically state that “the presence or absence of odorous or cloudy urine should NOT be used as an indication for urine culture or antimicrobial therapy” and “the presence, absence or degree of pyuria should NOT be interpreted as an indication for antimicrobial treatment.” If a subject presents with any of these symptoms and there are $\geq 10^3$ cfu/hpf bacterial growth on urine culture, the subject will be excluded and treated for a UTI according to clinical best practice.

Participant Burden:

Urine samples for urinalysis, urine culture and metagenomic sequencing will be obtained at up to monthly for the first year of study participation when not experiencing symptoms, at up to 2 occurrences of urinary symptoms during SMP_{PRO} intervention phase, and follow-up after either lactobacillus treatment or antibiotics and at follow-up, for a total of up to 18 samples per patient depending on the frequency with which urinary symptoms are experienced. When possible, our Research Assistant will meet with the patient at a mutually convenient location.

Baseline Data Collection:

Per IRB protocol # 2014-211 phase II, after consent, participants will complete the Health History Questionnaire, Urinary Symptom Questionnaire, In addition to questionnaires, all participants will provide a urine sample using sterile catheterization techniques. Thereafter, participants will complete the Urinary Symptom Questionnaire weekly.

Intervention:

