After 6 months of baseline data collection the intervention phase will begin. Prior to implementing the intervention protocol, participants will provide study staff with a urine sample either at MedStar NRH, CNMC, or when possible, the study RA will meet with the participant at a mutually convenient location. After urine sample is collected, study participants will follow the study protocol and complete USQ-NB weekly. If/when urinary symptoms occur, they will be instructed to follow the SMP_{PRO} protocol to determine whether to initiate intravesicular *Lactobacillus* instillation or be evaluated by a physician. The self-management protocol (SMP_{PRO}) will also direct them to discontinue *Lactobacillus* instillation or be evaluated by a physician if symptoms remit, persist or worsen. If participants are directed by the self-management protocol to seek medical attention or s/he feels the need for medical evaluation, s/he will be advised to obtain care as they typically would by their health care provider. Participants will be supplied with letters to be brought to their health care provider notifying them of the study and requesting sharing of urinalysis and urine culture results with the research team. A verified UTI will include those that resulted in antibiotic treatment by a health care professional. An additional urine sample for metagenomics will either be left with the health care provider for pick up by the research team, brought to the research site, or obtained by the RA at a mutually convenient site. If participant is treating urinary symptoms at home with *Lactobacillus*, a urine sample will be dropped off either at MedStar NRH, CNMC or when possible, the study RA will meet with the participant at a mutually convenient location.

The Impact of Self-Management with Probiotics on Urinary Symptoms and the Urine Microbiome in Individuals with Spinal Cord Injury and Spina Bifida Protocol

5/18/2017

Page 8 of 17

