H2. Compared with usual management, self-management of urinary symptoms with probiotics will reduce bladder inflammation (Secondary outcome). For those 20 participants in the subsample giving urine samples, bladder inflammation will be measured from each urine sample using a standard white blood count (WBC) from the urinalysis. WBC counts will be obtained only at the start of each timeframe, and so can be analyzed longitudinally as continuous variables representing the 6-month pre-treatment period and the 6 month-SMP_{PRO} period. As such we plan a mixed effects linear regression model of WBC counts with time treated as the factor of interest. This analysis will assess whether WBC is significantly different from the SMP_{PRO}, and post-SMP_{PRO}, relative to the baseline pre-treatment periods.

H3. Compared with usual management, self-management of urinary symptoms with probiotics will reduce the need for antibiotics to treat UTI (Secondary outcome). The number of times antibiotics are used for each patient will be obtained from their medical records or self report. This value will be analyzed with the same three-point longitudinal mixed effects regression model with time as the factor of interest. Depending on the distribution of the outcome (i.e. given the count nature of this outcome, it may be Poisson distributed), we will utilize either linear or Poisson regression models. This analysis will assess whether there is an association between UTI rate during use of the SMP_{PRO}, and post-SMP_{PRO} exposure, relative to UTI rate during the baseline pre-treatment period.

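### H2 compares SMP with baseline using two urine samples that both precede any instillation, so that contrast cannot show an SMP effect on bladder inflammation

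*Combined protocol and SAP*

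**What the plan says.** The H2 paragraph makes two statements about which samples count. The first is that "bladder inflammation will be measured from each urine sample using a standard white blood count (WBC) from the urinalysis". The next sentence says "WBC counts will be obtained only at the start of each timeframe". The planned mixed model follows from the second: the start-of-timeframe values are taken to represent the six months before treatment and the six SMP months, and the SMP and post-SMP values are compared with baseline.

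The Phase III sections give the timing. Under Intervention, after six months of baseline, "Prior to implementing the intervention protocol, participants will provide study staff with a urine sample". Use of the SMP then depends on symptoms: "If/when urinary symptoms occur, they will be instructed to follow the SMP_{PRO} protocol". Under Participant Burden, routine urine is collected "up to monthly for the first year of study participation when not experiencing symptoms". Further samples are taken "at up to 2 occurrences of urinary symptoms during SMP_{PRO} intervention phase" and after treatment with Lactobacillus or antibiotics. All of these include urinalysis, up to 18 samples per person. The opening paragraph of Phase III describes the symptomatic samples without naming a phase: "up to two times when subject experience urinary symptoms".

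**The concern.** A value that represents the SMP period should be able to carry an effect of the SMP. The value H2 assigns to that period is collected at its threshold, before the participant has had any occasion to instil. H2 would then test the six months of usual care that have just ended, under the label of the SMP.

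Either result could mislead. A null contrast would be read as no effect on inflammation, when the treatment had not begun. A significant contrast would be read as a benefit, when it could reflect only change over six months of usual care, or chance. Meanwhile the routine urinalyses collected while the SMP is in use would stay out of the model.

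**Working it through.** H2 states no power, sample-size, mean or standard deviation figure for WBC, so there is no plan figure to reproduce. The check is of timing and sample counts.

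1. **Timeline of the H2 values.**
   - Start of baseline: the enrolment sample (Phase III, Baseline Data Collection), month 0, usual care.
   - Start of SMP: the pre-intervention sample (Phase III, Intervention), about month 6, before the intervention protocol is put into use. Kits are supplied only after six months of baseline (Phase II, Intervention), and Phase III participants are enrolled in Phase II.
   - Start of follow-up: about month 12. No sample is named for this point. The opening of Phase III places the follow-up sample three months into follow-up, and Post-Intervention Follow-Up places one at the end. A month-12 routine sample could serve.

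2. **The SMP-versus-baseline contrast.** Write a participant's WBC at month t, on whatever scale is modelled, as Y(t) = b + u(t) + d(t) + error. Here b is the person's own level, u(t) is change under usual care, and d(t) is the effect of SMP use. Before any instillation, d(t) = 0. Then
   E[Y(6) − Y(0)] = [b + u(6) + 0] − [b + u(0) + 0] = u(6) − u(0).
   The treatment term is absent. If usual care is stable, the expected difference is 0 and the test rejects only at its nominal rate. This does not depend on the number of participants (H2 says 20, Phase III says 30, H4 says 50) or on symptom state at sampling.

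3. **The post-SMP contrast.** E[Y(12) − Y(0)] = u(12) − u(0) + d(12). This can carry an effect, but one sample at or after the end of the SMP period shows only what persists beyond the episodes in which the SMP was used.

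4. **How much of the planned urine H2 uses.** Up to 12 routine + 2 symptomatic + 2 post-treatment + 1 follow-up = 17. Counting both described follow-up samples gives 18, the stated maximum. H2 as worded uses at most 3, and 3/18 = 17%.

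5. **What the routine samples would add.** If the 12 routine samples split evenly at month 6, the model would have up to 6 baseline + 6 SMP + 1 follow-up = 13 values per person, instead of 3. The split depends on whether the enrolment and pre-intervention samples count among the 12, which the plan does not say. The SMP-period mean would then include values of d(t) from months when the SMP was available.

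**The case against.** The best defence is the sentence that opens the H2 analysis, which refers to every urine sample. On that reading, on-treatment urinalyses do enter and the defect disappears. But the next sentence says otherwise, and the model is built on it. The plan cannot be run both ways, so the contradiction has to be settled.

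A second defence is that between-episode WBC is a legitimate target. Phase Ia asks whether instilled Lactobacillus persists in urine, and a lasting fall could appear in the post-SMP sample. That is right, and it is why the point is confined to the SMP-versus-baseline contrast. It is also fair that H2 is secondary in a pilot, and that fewer episodes would show through UTI counts in H1 and antibiotic use in H3.

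A reader might go further and infer that all H2 samples are symptom-free, so that H2 is bound to miss any change in inflammation. The documents do not support this. Symptom-free status is stated for the routine monthly samples only. The enrolment, pre-intervention and follow-up samples carry no such condition, and entry excludes current or recent UTI rather than all symptoms.

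A reader might also want to test H2 on the change from symptomatic to post-treatment sample. WBC may fall as an episode resolves by itself. Participant Burden places symptomatic samples in the intervention phase, so there may be no usual-care comparator; the Phase III opening leaves the phase open. Lactobacillus versus antibiotics would also be confounded by severity, because persistent or worsening symptoms lead to medical care.

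**Conclusion.** The point holds in this form: under the start-of-timeframe sentence, the SMP-versus-baseline contrast in H2 compares two pre-instillation samples and has an expected treatment effect of zero. Only a later sample could show an effect, and then only one that lasts between episodes.

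The conclusion rests on two things the documents state: the opening SMP sample precedes the intervention protocol, and the SMP is symptom-triggered. It needs no assumption about WBC levels, episode length or symptom state. No size is given for inflammation missed during episodes, because the documents contain no WBC figures from which to derive one.

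It does not follow that H2 as a whole is uninformative, or that episode samples would supply a valid test against usual management. The change is worth making because it alters what H2 can conclude and uses urinalyses already planned.

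**What to change.** - **Reconcile the two H2 sentences** and name the samples that enter the model, with their timing relative to SMP start and their symptom state. Say that symptom-free status is specified for the routine monthly samples but not for the enrolment, pre-intervention or follow-up samples.
- **Fit the H2 mixed model to all routine (up to monthly) urinalyses.** Assign months 1–6, including the pre-intervention sample, to baseline; samples after the SMP starts through month 12 to the SMP period; and the follow-up sample to post-SMP. Keep a random subject intercept. State whether the follow-up sample is at three months, at the end, or both.
- **Word the H2 conclusion as routine, between-episode WBC.**
- **Report WBC in symptomatic and post-treatment samples descriptively only,** labelled as uncontrolled data from within the intervention period and not as a test of H2 against usual management.

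The cost is plan wording and a model on urinalyses already scheduled, with no added samples or visits. There are two downsides: the number of routine samples per person will vary, and the between-episode measure still does not capture inflammation during episodes. The differing subsample sizes (20, 30 and 50) also need reconciling, but that is a separate matter.

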Intervention: After 6 months of baseline data collection, participants will receive the *Lactobacillus* (Culturelle) kits. Participants will be instructed on preparation and intravesicular instillation of the *Lactobacillus*, and will have a tutorial with a fellow consumer on use of the patient-initiated SMP_{PRO}. Participants will receive 10 Culturelle tablets the beginning of the

The Impact of Self-Management with Probiotics on Urinary Symptoms and the Urine Microbiome in Individuals with Spinal Cord Injury and Spina Bifida Protocol

5/18/2017

Page 5 of 17

treatment phase. At the end of each week, the coordinator or RA will ask how many remaining tablets the participant has and will instruct them to complete the USQ-NB weekly. If/when urinary symptoms occur, they will be instructed to follow the SMP_{PRO} protocol to determine whether to initiate intravesicular *Lactobacillus* instillation or to seek medical attention. The self-management protocol will also direct them to discontinue *Lactobacillus* instillation or to seek medical attention if symptoms remit, persist or worsen. If participants are directed by the self-management protocol to seek medical attention or s/he feels the need for medical evaluation, s/he will be advised to obtain care as they typically would by their health care provider. Participants will be supplied with letters to be brought to their health care provider notifying them of the study and requesting sharing of urinalysis and urine culture results with the research team. A verified UTI will include those that resulted in antibiotic treatment prescribed by a health care professional.

For the intravesicular *Lactobacillus* instillation, the contents of 1 *Lactobacillus* capsule will be mixed into 45 cc sterile 0.9% saline (adult bladder volume is 450cc, representing 10% of adult bladder volume). After mixing, study participants will draw up the 45 cc of the liquid *Lactobacillus* mixture into a 60cc catheter tip syringe and instill via the intermittent catheter using sterile technique. For children volume is based on age (see table on page 4 of protocol).

Study participant will recheck symptoms after 24 hrs (valid range 22-30 hrs) following the SMP_{PRO} protocol and either perform another *Lactobacillus* instillation or seek medical attention, per the subjects choice. If symptoms still persist 4 hrs after second instillation, study participants are instructed to seek medical attention.

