To determine whether bacterial diversity differs between study groups the Shannon Diversity Index will be used. The Shannon Index is a measure of sample diversity that takes into account total number of bacterial types in the sample and relative proportion of the bacterial types. From the subsample of 50 participants giving urine samples, subjects who did in fact utilize the SMP at least once during the 6-month SMP time frame will be stratified into two groups, those who responded to SMP and those who did not; we will define "response" as the observation of a 10% or more decrease in the average number of USQ items endorsed within any time frame, so that each of the 50 persons in this sub-sample will be characterized as either a responder (10% or more decrease) or a non-responder (0-9.99% decrease). A scatter plot of response group versus Shannon Index will be produced, and a mixed effects linear regression model will test the individual (main) and interaction effects of response group and time on Shannon Index. A positive time coefficient is indicative of increased microbiome diversity and a negative time coefficient indicates reduces diversity. The magnitude of difference between the response groups will be determined using the Yue-Clayton theta similarity index (θ). The θ index measures the difference in the number and relative abundance of bacterial species between samples^{4,5} when $\theta=1$ two samples have identical community structure and when $\theta=0$ indicates complete dissimilarity between samples. Pathoscope will be used to calculate abundance of different taxonomic groups at each time point.

REFERENCES

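### H4 names two analysis populations in one sentence, and the users-only one is selected on symptoms during the intervention period, which lowers baseline-to-SMP symptom response and can distort the Shannon results in an unknown direction

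*Combined protocol and SAP*

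**What the plan says.** The H4 paragraph on the Shannon Diversity Index starts from the urine subsample and restricts it: "subjects who did in fact utilize the SMP at least once during the 6-month SMP time frame will be stratified into two groups". The same sentence ends by covering everyone: "each of the 50 persons in this sub-sample will be characterized as either a responder (10% or more decrease) or a non-responder (0-9.99% decrease". Response is "the observation of a 10% or more decrease in the average number of USQ items endorsed within any time frame", with no reference period named. The model follows: "a mixed effects linear regression model will test the individual (main) and interaction effects of response group and time on Shannon Index". Its time coefficient is read only as more or less diversity: "A positive time coefficient is indicative of increased microbiome diversity and a negative time coefficient indicates reduces diversity".

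The Intervention sections of Phases II and III tie use of the SMP to symptoms: "If/when urinary symptoms occur, they will be instructed to follow the SMP_{PRO} protocol to determine whether to initiate intravesicular" *Lactobacillus* or to go for medical care. H4 itself asks how self-management compares with usual management, and its stated goal is a microbiome restored to its baseline state.

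**The concern.** Two analysts could follow this sentence faithfully and analyse different people. The choice matters because the users-only set depends on what happens after baseline. A participant stays in it only if symptoms arose during the intervention period, and nothing comparable is required of the baseline or follow-up period. Someone who stays symptom-free through the intervention period, the best outcome the SMP could have, is left out.

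Selecting on an event in one period makes that period look more symptomatic than its neighbours even when nothing has changed. The symptom label that stratifies the Shannon model then partly reflects selection. A set chosen in this way cannot cleanly answer a comparison with usual management.

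**Working it through.** The plan gives no sample size, power or effect figure for H4, so there is none to reproduce. The check asks how far the two populations differ and what the users-only filter does when the SMP has no effect.

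**Inputs**
- Entry requires at least 2 UTIs in the past year (Phase III inclusion criteria), which is 1 per 6 months if spread evenly.
- The power calculation takes a baseline mean of 6 UTIs per 6 months and an SD of 4. Its 4.75 is the mean after the hypothesised reduction, so it is not used as a no-effect rate.
- The subsample is 50 in H4 and 30 in Phase III (H2 says 20).
- Assumptions: UTIs stand in for symptom episodes, each episode leads to SMP use, and the episode rate is the same in every period.

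**Share who never use the SMP**
- Poisson, P(0) = exp(−m). At m = 1: 0.368, or 18.4 of 50 and 11.0 of 30. At m = 2: 0.135, or 6.8 of 50 and 4.1 of 30.
- Negative binomial with mean 6 and variance 16: k = 36/(16 − 6) = 3.6, so P(0) = (3.6/9.6)^3.6 = 0.029, or 1.5 of 50 and 0.9 of 30.

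**Mean episodes among users, Poisson**
- SMP-period mean = m/(1 − P(0)). At m = 1 this is 1/0.632 = 1.58, against 1.00 at baseline and at follow-up. At m = 2 it is 2/0.865 = 2.31, against 2.00.

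**Share with a fall of 10% or more, Poisson counts**

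With small counts this is essentially P(later < earlier) = (1 − P(equal))/2.
- m = 1, everyone: (1 − 0.3085)/2 = 0.346.
- m = 1, users, baseline to SMP: remove the cases with no SMP-period episode and at least one at baseline, then divide by the share of users. (0.346 − 0.368 × 0.632)/0.632 = 0.179.
- m = 1, users, SMP to follow-up: 0.346/0.632 = 0.547.
- m = 2: everyone (1 − 0.207)/2 = 0.396. Users, baseline to SMP: (0.396 − 0.135 × 0.865)/0.865 = 0.323.

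So at m = 1 the filter takes baseline-to-SMP response from 35% down to 18%, and SMP-to-follow-up response from 35% up to 55%.

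**On the plan's own scale.** Response is defined on average USQ-NB items, not on episode counts. A no-effect simulation of about 400,000 people assumed about 3 background items (SD 1), 10 extra items in an episode week and 26 weeks per period.

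| Episodes per 6 months | Comparison | Everyone | Users only |
|---|---|---|---|
| 1 (Poisson) | Baseline to SMP | 30% | 18% |
| 1 (Poisson) | SMP to follow-up | 30% | 42% |
| 1 (Poisson) | Baseline to SMP, or baseline to follow-up | 44% | 37% |
| 1 (Poisson) | Baseline to SMP, or SMP to follow-up | 57% | 56% |
| 1 (overdispersed, gamma shape 1) | Baseline to SMP, or SMP to follow-up | 54% | 57% |
| 6 (SD 4) | Baseline to SMP | 34% | 33% |

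**Shannon Index.** Nothing in the documents links symptoms to diversity numerically, so no size can be computed. There is a route for the selection to enter. Phase III (Participant Burden) schedules extra urine samples at up to 2 symptomatic occurrences in the intervention phase, and the filter keeps the people who can contribute them.

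**Classes.** The non-responder class runs from 0 to 9.99% decrease. Anyone whose average rises has no class, so the promise to classify each person cannot be kept as written.

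**The case against.** A reader might infer that the users-only filter biases H4 against the SMP. The documents do not support that as a general statement. It holds for baseline-to-SMP symptom change. SMP-to-follow-up change is pushed the other way, and since the plan fixes no reference period, the net effect on response can be close to nil or reversed, as the table shows. For the Shannon Index no direction of change is called a benefit, so no direction can count against the SMP.

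A reader might also quote a larger contrast. Among people with at least one baseline episode, the Poisson model at rate 1 gives 54.7% falling to 28.3%. That condition adds its own regression to the mean, and the plan does not impose it.

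The size can be challenged too. An eligibility minimum for UTIs is not everyone's mean symptom rate, and symptoms short of a treated UTI can trigger the SMP. The power calculation supposes an average of 25 items endorsed at baseline. If that is realistic, few people would go 6 months without using the SMP. Against this, if using the SMP means instilling, non-use would be higher, because the SMP can direct people to medical care instead, and its introduction also lists fluids. The plan does not define use.

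Finally, labelling someone who never used the SMP as a responder to it makes little sense, so simply deleting the filter would create a new fault. This stands, and the fix allows for it. H4 is also a secondary analysis in a pilot, and H1 is evaluated in all pilot participants, so symptom-free people still count in the primary comparison. These points limit size and direction. They leave the conflict between the two populations and the post-baseline selection in place.

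**Conclusion.** The point holds in limited form. H4 specifies two populations, and the users-only one is selected on symptoms in the intervention period. With no true effect, that selection lowers baseline-to-SMP symptom response, raises SMP-to-follow-up response, and can distort the Shannon time and group effects with a sign that the documents do not determine.

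The two sets could differ by over a third of the subsample at 1 episode per 6 months, or be almost the same set at the plan's 6 UTIs per 6 months with SD 4. These figures rest on UTIs standing in for episodes, on each episode leading to use, and on a constant rate. The contradiction in the text and the unclassified people who worsen depend on none of these. Correcting the wording before analysis is worthwhile and proportionate for a secondary outcome.

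**What to change.** - Fit the main H4 model of the Shannon Index over time in every Phase III participant with a baseline and a later sample. Remove the condition of having used the SMP at least once.
- Classify symptom change for everyone as SMP period versus baseline: a fall of 10% or more in one class; any smaller fall, no change or worsening in the other.
- Call this symptom improvement rather than response to the SMP, so that people who never used it are not labelled as responding to it.
- Define what counts as using the SMP, and report users, split by response, as a descriptive secondary analysis.
- State one subsample size in H2, H4 and Phase III.

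The cost is a change to the analysis wording, with no new data. The downside is that the all-participant contrast is diluted by people who never used the SMP. The descriptive users-only analysis shows users separately.
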